5. GENERAL ANALYSIS CONSIDERATIONS

The statistical analyses will be reported using summary tables and listings (TLs). The International Conference on Harmonization (ICH) numbering convention will be used for all TLs. Continuous variables will be summarized with means, standard deviations, medians, minimums, and maximums. Categorical variables will be summarized by counts and by percentage of subjects in corresponding categories. Percentages for missing values are omitted and do not account for the percent calculation of other categories. Percentages are routinely based on the total category count excluding the missing category if not otherwise mentioned. Percentages showing a rate relative to the total number of subjects in this group are given in special tables (e.g. AE tables). Footnotes will specify the percent basis. All summary tables will be presented by cohort and dose level. Baseline summaries will also include a total summary column. Unless otherwise noted, baseline is defined as the value obtained at the baseline visit. If the baseline value is missing, the baseline value will be the last non-missing value recorded prior to the first dose of study drug.

Individual subject data obtained from the case report forms (CRFs) and derived data will be presented by subject in data listings.

jCyte, Inc	Statistical Analysis Plan
Protocol No. JC-01	08Nov2017

The analyses described in this plan are considered *a priori*, in that they have been defined prior to database lock. Post-hoc analyses will be labeled as such on the output and identified in the CSR.

All analyses and tabulations will be performed using SAS[®] Version 9.4 or higher. Tables, listings, and figures will be presented in RTF format. Upon completion, all SAS[®] programs will be validated by an independent programmer. In addition, all program output will undergo a senior level statistical review. The validation process will be used to confirm that statistically valid methods have been implemented and that all data manipulations and calculations are accurate. Checks will be made to ensure accuracy, consistency with this plan, consistency within tables, and consistency between tables and corresponding data listings. Upon completion of validation and quality review procedures, all documentation will be collected and filed by the project statistician or designee.

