10.3 Clinical Laboratory Evaluation

Hematology, serum chemistry and coagulation laboratory parameters will be summarized using descriptive statistics at baseline, Day 7, Day 28, Month 3, Month 6, and Month 12/Early Term. Change from baseline in the laboratory parameters will also be presented, Unless otherwise noted, baseline is defined as the value obtained at the baseline visit. If the baseline value is missing, the baseline value will be the last nonmissing value recorded prior to the first dose of study drug.

No concerns are expected regarding the drug for laboratory results since the drug is expected to stay in the eye. As a result, no analysis using high/low flags will be carried out.

Urinalysis results will not be summarized but will be provided in data listing. Separate listing of abnormal clinically significant lab values and ECG interpretation will be presented.

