	14.3.4.8.1	Intraocular Pressure (IOP): Study Eye (Safety Population)
	14.3.4.8.2	Intraocular Pressure (IOP): Non-Study Eye (Safety
		Population)
	14.3.4.9.1	B-Scan : Study Eye (Safety Population)
	14.3.4.9.2	B-Scan: Non-Study Eye (Safety Population)
	14.3.4.10.1	Dilated Fundoscopic Examination: Study Eye (Safety
		Population)
	14.3.4.10.2	Dilated Fundoscopic Examination: Non-Study Eye (Safety
		Population)
	14.3.4.11	Post Injection Clinical Vitreous Exam: Study Eye (Safety
		Population)
	14.3.4.12.1	Optical Coherence Tomography (OCT): Study Eye,
		Categorical Analysis (ITT Population)
	14.3.4.12.2	Optical Coherence Tomography (OCT): Non-Study Eye,
		Categorical Analysis (ITT Population)
14.3	14.3.4.13.1	Fluorescein Angiography: Study Eye, Categorical Analysis
		(ITT Population)
	14.3.4.13.2	Fluorescein Angiography: Non-Study Eye, Categorical
		Analysis (ITT Population)
	14.3.4.14.1	Autofluorescence: Study Eye (ITT Population)

jCyte, Inc.		Statistical Analysis Pla	an
Protocol: JC-0	1	08Nov20	17
ICH Heading	Table Number	Table Description	
	14.3.4.14.2	Autofluorescence: Non-Study Eye (ITT Population)	

jCyte, Inc. Protocol: JC-01

List of Data Listings

ICH	Listing	
Heading	Number	Listing Description
16.2.1	16.2.1.1	Subject Disposition
16.2.2	16.2.2.1	Protocol Deviations
	16.2.2.2	Inclusion/Exclusion Criteria
16.2.4	16.2.4.1	Demographics and Baseline Characteristics
	16.2.4.2	Medical History
	16.2.4.3	Ocular Medical History
	16.2.4.4	Urine Drug Screen
	16.2.4.5	Infectious Disease Tests
16.2.5	16.2.5	Study Drug Administration
16.2.6	16.2.6.1	Best Corrected Visual Acuity (ETDRS)
	16.2.6.2	Electroretinogram
	16.2.6.3	Optical Coherence Tomography (OCT)
	16.2.6.4	Fluorescein Angiography
	16.2.6.5	Autofluorescence
	16.2.6.6	Visual Field Examination
16.2.7	16.2.7.1	Adverse Events
	16.2.7.2	Serious Adverse Events
	16.2.7.3	Related Adverse Events
	16.2.7.4	Post Injection Clinical Vitreous Exam
16.2.8	16.2.8.1	Hematology
	16.2.8.2	Chemistry
	16.2.8.3	Coagulation
	16.2.8.4	Urinalysis
	16.2.8.5	Clinically Significant Lab Values
	16.2.8.6	Vital Signs
	16.2.8.7.1	12-Lead Electrocardiogram
	16.2.8.7.2	Clinically Significant 12-Lead Electrocardiogram
		Interpretation
	16.2.8.8	Physical Examination
	16.2.8.9	Prior and Concomitant Medications
	16.2.8.10	Pregnancy Test
	16.2.8.11	PRA and DRA Antibody Test Results Received
	16.2.8.12	HLA Antibody Testing
	16.2.8.13	RP Gene Mutation Recieved
	16.2.8.14.1	Slit Lamp (OS)

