Cohort 1 - 0.5 x 10 ⁶ hRPC	XXXXXX	Screening Baseline Month 12 or Early Termination	Date9. (xx) Date9. (xx) Date9. (xx)	Positive/Negative Positive/Negative Positive/Negative	Yes/No Yes/No Yes/No	Positive/Negative Positive/Negative Positive/Negative

Cohort 2 - 0.5×10^6 hRPC	XXXXXX	Not Done: Reason

.

path\l_program.sas date time

Programmer Note: If NO marked for urine collection, include reason in "Urine Pregnancy Collection Date" column.

jCyte, Inc Protocol No. JC-01

Treatment Group	Subject ID	Visit	Collection Date (Study Day)	Sample Collected
Cohort 1 - 0.5 x 10 ⁶ hRPC	XXXXXX	Baseline Day 14 Day 28 Month 12 or Early Termination	Date9. (xx) Date9. (xx) Date9. (xx) Date9. (xx)	Yes/No Yes/No Yes/No
Cohort 2 - 0.5 x 10 ⁶ hRPC	XXXXXX			

Listing 16.2.8.11 PRA and DRA Antibody Test Results Received

path\l_program.sas date time

Programmer Note: If a panel/donor reactive antibody sample was not collected, please display "Not Done" and the reason in the "Collection Date/Time" column.

jCyte, Inc Protocol No. JC-01

			Joury Lessing		
Treatment Group	Subject ID	Visit	Collection Date (Study Day)	Result	Other HLA Antibody Testing Results/Reason
Cohort 1 - 0.5 x 10 ⁶ hRPC	XXXXXX	Screening Baseline	Date9. (xx)	XXXXXX	
Cohort 2 - 0.5 x 10 ⁶ hRPC	XXXXXX	Screening Baseline	Date9. (xx) Date9. (xx)	XXXXXX XXXXXX	

Listing 16.2.8.12 HLA Antibody Testing

path\l_program.sas date time

Programmer Note: If a HLA antibody testing sample was not collected, please display "Not Done" and the reason in the "Collection Date" column.

Page 102/120

CONFIDENTIAL RUC SAP 08Nov2017.docx

Listing 16.2.8.13 RP Gene Mutation Received

Treatment Group	Subject ID	Collection Date (Study Day)	Sample Collected
Cohort 1 - 0.5 x 10 ⁶ hRPC	XXXXXX	Date9. (xx) Date9. (xx) Date9. (xx)	

Cohort 2 - 0.5 x 10⁶ hRPC

XXX--XXX

.

path\l_program.sas date time

Programmer Note: For Other Row, show either Subject or Related under HLAA Typing Result column

Listing 16.2.8.14.1 Slit Lamp Exam (OD) Part 1 of 2

T 4 40	Subject	X 7° °4	Exam Date (Study		Change from Previous		Change from Previous		Change from Previous	0.1	Change from Previous		Change from Previous
Treatment Group	ID	VISIT	Day)	Eyelids	VISIT?	Eyelashes	VISIU?	Conjunctiva	V1S1U?	Sciera	V1S11?	Cornea	VISIT?
Cohort 1 - 0.5 x 10 ⁶ hRPC	xxxxxx	Screening	Date9.(xx)	Normal		Normal		Normal		Normal		Normal	
		Baseline	Not Done: Reason	Abnormal CS	Yes	Abnormal CS	SYes	Abnormal CS	SYes	Abnormal C	CS Yes	Abnormal C	2S Yes

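### PRA/DRA antibodies are a scheduled safety assessment, but the only SAP output for them, Listing 16.2.8.11, shows that a sample was taken and not its result

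*SAP*

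**What the plan says.** **Protocol.** The synopsis, under the safety criteria for evaluation, includes anti-drug antibodies. Section 8.1.4 and Table 2 (with its footnote on the two assays) place PRA and DRA samples at four times: baseline, Day 14, Day 28 and Month 12 or early termination. The visit lists in sections 7.2, 7.5.4, 7.5.6 and 7.6 agree. Section 9.1 gives antibody development as one example of an adverse event.

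**SAP text.** Section 10.3 states: "Hematology, serum chemistry and coagulation laboratory parameters will be summarized using descriptive statistics". Urinalysis is listed only. Antibodies are not mentioned there or anywhere else in section 10. On limiting the laboratory analysis, 10.3 reasons that the product should stay in the eye and concludes: "As a result, no analysis using high/low flags will be carried out".

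**SAP outputs.** Appendix B has no antibody table. Its listing index contains "PRA and DRA Antibody Test Results Received". The Appendix D layout of that listing, headed "Listing 16.2.8.11 PRA and DRA Antibody Test Results Received", has five columns: treatment group, subject, visit, collection date with study day, and "Sample Collected", filled with Yes or No. The programmer note opens "If a panel/donor reactive antibody sample was not collected" and deals only with that case.

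**The concern.** Safety and tolerability are the primary objective. The cells are allogeneic, the protocol bars immunosuppressants other than the topical steroids, and Protocol 3.2.2 makes absence of overt immune rejection a safety criterion. PRA/DRA is the only antibody assay scheduled after treatment. A title that promises results over columns that record only collection leaves the programmer with two readings. Followed literally, the layout would put into the clinical study report the fact that blood was drawn and leave out what the assays showed. A subject who stayed antibody-negative and one who turned positive without an adverse event being recorded would look the same.

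**Working it through.** The plan states no figure on this point, so the check is a cross-reference of scheduled data against planned outputs, plus a count.

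**1. Scheduled occasions.** The protocol plans up to 28 subjects, 14 per cohort, with dose cells of 4, 4, 3 and 3. There are four sampling times, of which three follow treatment.

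- All occasions: 28 × 4 = 112.
- Post-treatment: 28 × 3 = 84.
- Check by cell, per cohort: 4 × 3 + 4 × 3 + 3 × 3 + 3 × 3 = 12 + 12 + 9 + 9 = 42. Two cohorts: 2 × 42 = 84.

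These are ceilings: full enrolment, no missed visits.

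**2. Planned outputs that could hold a post-treatment PRA/DRA result.**

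| Place in SAP | What it would show |
|---|---|
| Section 10.3 | Hematology, chemistry, coagulation; urinalysis in a listing |
| Rest of section 10 | No antibody analysis |
| Appendix B tables | None for antibodies; the laboratory tables end with coagulation (14.3.4.3) |
| Listing 16.2.8.11 | The four correct visits; collection Yes/No; no result column |
| TEAE tables and AE listings | Antibody development only if reported as an adverse event |

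Tables with a PRA/DRA result: 0. Listing layouts with a post-treatment PRA/DRA result column: 0.

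**3. Could a column have been lost in text extraction?** This is unlikely. The header row is intact and the programmer note fits a collection-only listing. Listing 16.2.8.13, on gene mutation, has a similar receipt-type layout. The neighbouring pregnancy-test listing (16.2.8.10) and "Listing 16.2.8.12 HLA Antibody Testing" (16.2.8.12) both keep their result columns.

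**4. Does SAP 10.3 explain the omission?** No. Its stated reason is attached to high/low flags on routine laboratory values. It does not address antibodies to donor cells.

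**The case against.** The case on the other side has substance.

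- *General listing commitment.* SAP section 5 says: "Individual subject data obtained from the case report forms (CRFs) and derived data will be presented by subject in data listings". If assay results are on the CRF, this covers a listing of them. The documents do not say whether they are. Protocol 8.1.4 refers to shipping samples, so a separate laboratory file is possible. Even on the CRF, the layout drawn for these data has nowhere to print a result.
- *Programming flexibility.* Appendix A lets variables be added to listings, and Appendix B says minor changes to the index need no SAP amendment. This stands, and it makes the repair easy. It does not specify a result column.
- *Adverse event route.* A reported case of antibody development would reach the TEAE tables. This also stands. But the documents give no rule for when a PRA or DRA change becomes an adverse event, and those tables carry no baseline antibody status.
- *The HLA listing.* Listing 16.2.8.12 has a result column but shows only Screening and Baseline. A reader might infer that post-treatment results are excluded from it by design. The rows do not support that: the BCVA layout omits Month 5, the OCT layout Month 9 and the vital-signs layout Month 6, all scheduled in Protocol Table 2. The shells are rough, and the protocol schedules HLA typing rather than HLA antibody testing, so this listing is weak evidence either way.
- *Need for a table.* Protocol 3.2.2 does not name antibodies, Protocol 10.3 promises only adverse event and laboratory statistics, and the SAP leaves urinalysis and physical examination to listings. With three or four subjects per cell, a result listing shows everything. This is fair, and it makes the table secondary to the listing.

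**Conclusion.** The point holds in a limited form. A safety assessment named and scheduled in the protocol has no planned output for its assay results: up to 84 post-treatment sampling occasions at full enrolment without missed visits. The title and columns of Listing 16.2.8.11 need to be reconciled. The conclusion rests on reading the listing layout as printed.

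Two stronger readings are tempting, and the documents do not support them.

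- A reader might infer that the report could not separate sampled from unsampled subjects. It could: the listing gives collection by subject and visit, and Not Done with a reason otherwise. Collection does not prove that an assay was run, but what is missing is the result, not the sampling count.
- A reader might infer that no antibody finding could reach the report at all. Cases reported as adverse events would.

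Nor do the documents show that results were meant to be withheld. They leave the matter unspecified.

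**What to change.** 1. In Listing 16.2.8.11, add PRA and DRA result columns at each of the four visits, so that the layout matches the title.
2. In SAP 10.3, add a short descriptive count in the Safety population, by cohort and dose level, for PRA and DRA separately: number with a result, status at baseline, and number newly positive (negative at baseline) at Day 14, Day 28 and Month 12 or early termination. State the testing laboratory's definition of positive, which neither document gives.
3. If the table is judged unnecessary at three or four subjects per cell, the first change alone closes the main gap.

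The cost is one listing change, one small table and no new sampling. If the results sit in a laboratory file outside the CRF database, they must be transferred and merged; the documents do not show whether this applies. Anything added after database lock should be labelled post hoc, as SAP section 5 requires.

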10 IIKFC

Note: With respect to "Vitreous Exam", "Optic Nerve Exam", "Macula Exam", and "Peripheral Retina Exam" columns, CS=Clinically Significant, NCS=Not Clinically Significant. path\l program.sas date time

Programmer Note: Sorting order is by Cohort #, subject ID, examination date (include unscheduled visits in the date sequence), and examination time.

Programmer Note: If dilated funduscopic examination was not performed, please display "Not Done" and the reason in the "Examination Date/Time" column

This page intentionally left blank
